6.2.3 Adverse Events

An adverse event (AE) is defined as any untoward medical occurrence associated with the use of a drug in humans, whether or not considered drug related. An AE can therefore be any unfavorable and unintended sign (including an abnormal laboratory finding, for example), symptom, or disease temporally associated with the use of a test article, whether or not considered related to the test article.

Any AE caused by a drug is an adverse drug reaction (ADR). ADRs are a subset of all suspected adverse reactions for which there is reason to conclude that the drug caused the event. Any AE for which there is a reasonable possibility that the drug caused the event is a suspected adverse reaction (SAR). Serious adverse events (SAE) are defined as any untoward medical occurrence that at any dose in the view of either the Investigator or Sponsor results in death, is life-threatening, requires inpatient hospitalization or prolongation of existing hospitalization, results in persistent or significant incapacity or substantial disruption of the ability to conduct normal life functions, or is a congenital anomaly/birth defect.

The AE and SAE reporting period starts following the subject's written consent to participate in the clinical trial with the first trial related procedure and ends after the last treatment dose. Throughout the clinical trial the subject will be questioned in a non-directive way as to the occurrence of adverse events. All adverse events which were not present at Screening will be recorded. Adverse events will be followed through the last day of the study, until the investigator determines outcome, stabilization, and/or resolution of the event, or not-relatedness to study medication, or up to 30 days after the last dose of study drug.

[figure not shown]
The severity of an AE will be recorded as mild, moderate or severe. The relationship between an AE and the test article will be classified as certain, probable, possible or not related. The AE outcome will be specified as not recovered/resolved, recovered/resolved, recovered/resolved with sequelae, recovering/resolving, fatal, or unknown.

6.2.4 Concomitant Medications and Concurrent Therapies/Procedures

Details of concomitant medication use and concurrent therapies/procedures will be collected for each subject.

7 DATA SETS ANALYZED

The Safety population will include all randomized subjects who received the test article. Subjects who were randomized and applied at least one dose oftest article and returned for at least one post-Baseline evaluation will be included in the intent-to-treat (ITT) population. Subjects who complete the two, 2-week cycles of treatment and all of the Visit 7 follow-up evaluations at Week 14 will be considered to have completed the study.

Efficacy summaries and analyses will be carried out in the ITT and PP populations. All summaries of safety will be carried out in the Safety population.

8 STATISTICAL METHODS

8.1 General Considerations

All statistical processing will be performed using SAS Version 9.4, unless otherwise noted. Continuous data will have the following summary statistics reported: number of subjects, mean, standard deviation, minimum and maximum. For categorical data, the number and percentage of subjects within each category will be reported.

All data will be listed in subject data listings sorted by treatment group, site and subject number unless otherwise noted. Data tabulations will be prepared as described in the sections below.

8.2 Efficacy Endpoints

8.2.1 Primary Endpoint

Complete clearance rate (treatment success) is defined as the proportion of subjects in a treatment group with a 100% clearance of all AK lesions within the Treatment Area. The primary endpoint is the proportion of subjects in the PP population with treatment success at Visit 7 (Week 14/ End of Study). All AKs (Baseline and new lesions), independent of size, within the Treatment Area will be included in the AK lesion count for each visit.

8.3 Safety Endpoints

8.3.1 Dosing Compliance

Measures of test article compliance will include the total number of days of test article applications recorded in the case report forms and verified from the data in the subject diaries. Compliant subjects are defined as those who apply at least 75% and no more than 125% of the test article applications and no other evidence of material dosing noncompliance.

8.3.2 Adverse Events and LSRs

The severity and frequency of adverse events and local skin reactions (LSRs) will be assessed in the three treatment groups.

8.4 Subject Disposition

All subjects enrolled into the study that are issued a subject number will be accounted for in Subject Disposition. Subjects who complete the two, 2-week cycles of treatment and all of the Visit 7 follow-up evaluations at Week 14 will be considered to have completed the study. Data will be tabulated by treatment group and the number and percentages of subjects in each treatment group who are enrolled, randomized and treated, who comprise the ITT population, who comprise the PP population, and who complete the study or withdraw prematurely along with the reason for discontinuation will be presented. The number of subjects who were seen at each assessment time point will also be tabulated.

The number of subjects who were screen failures will be tabulated by site and reason for screen failure.

All patients who drop out of the study will be listed. The listing will include, site number, subject number, reason for dropout, treatment group, last visit, and whether the subject was replaced.

Actavis Elizabeth LLC 8.5 Methods for Handling Missing Data

8.6 Screening and Baseline Assessments

8.6.1 Demographic and Baseline Characteristics

Gender, age (derived), race and ethnicity will be summarized by treatment group for the ITT and PP populations. The number in each of the following age groups will also be summarized by treatment group for the ITT and PP populations: 18-40, 41-64, 65-75, and >75. Age will be calculated as floor[(screening date - date ofbirth)/365.25].

The size of the Treatment Area (in centimeters) at Baseline will be determined from an estimate of the %BSA treated, the subject's height and weight using the Mosteller formula. Characteristics of the AK lesions in the Treatment Area at Baseline will be summarized including the total number of AK lesions and the number of AK lesions at least 4 mm in diameter.

Informed consent information and subject eligibility status will be provided in a listing.

8.6.2 Medical History and Dermatologic Exam

Medical history, including onset of actinic keratoses, will be presented in a subject data listing. Verbatim terms on the CRFs will be mapped into system organ class and preferred term using MedDRA Coding Dictionary version 16.0. Tabulations of the number of subjects reporting medical history events will be presented by System Organ Class (SOC), Preferred Term (PT), and treatment group. Abnormalities noted during the dermatologic exam, excluding AKs, will be provided in a listing.

8.6.3 Vital Signs

Systolic and diastolic blood pressures (mm Hg), pulse rate (beats/minute), temperature (°F), and respiration rate (breaths/minute), as well as, height (in) and weight (lbs) will be summarized by treatment group for the ITT population.

8.6.4 Prior Medications and Therapies/Procedures Identified in the Exclusion Criteria

Listings will be provided for the prior medications and therapies/procedures that needed a washout period prior to the subjects' enrollment.

8.6.5 Concomitant Medications and Concurrent Therapies/Procedures

Concomitant medications and concurrent therapies/procedures will be provided in separate subject listings. Concomitant medications will be coded using the WHO Drug dictionary (version effective 01 September 2012). The medications will be tabulated by treatment group, Drug Class (pharmacological level, ATC3) and Drug Name (chemical substance level, ATC5).

8.6.6 Dosing Compliance

Study medication dosing will be recorded daily during each of the two-week treatment cycles including the number of pump actuations applied per day with indications of whether or not the dose was missed or held. The number of applications, missed doses, held doses and percent of expected doses will be summarized by descriptive statistics for the ITT and PP populations. The percent of expected doses will be calculated using 28 (once daily dosing for two 14 day treatment cycles) as the expected number of doses. Compliant subjects are defined as those who apply at least 75% and no more than 125% of the expected test article applications.

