6.2 Instructions for Use and Application

Subjects will be instructed to apply test article once daily approximately 1 to 2 hours before bedtime to the skin of the treatment area (either full face (excluding the ears) or balding scalp) for two, 2-week treatment cycles separated by a 2-week no-treatment period. Subjects will apply test article for 14 consecutive days for each treatment cycle, regardless of the visit window. However, if a subject did not apply for 14 consecutive days due to a dose held or missed, and 14 consecutive days has elapsed from baseline, then no additional test article will be applied to make up for missed or held doses. Test article should be applied as a thin film to the entire treatment area and rubbed until the cream is no longer visible. Up to two (2) full actuations of the pump may be dispensed and applied to the treatment area at each application. Subjects will be cautioned to avoid applying the cream to the lips, nostrils and periocular areas. The test article should be left on the skin for approximately eight (8) hours, after which time the test article should be removed by washing the area with mild soap and water. Treatment should continue for

Sponsor Name: Actavis, LLC Protocol: 094-3153-301, v1.0

the full treatment course even if all AKs appear to be gone. The study staff should demonstrate the proper use of the pump and application technique using the pumps containing the vehicle cream provided for subject training. See **Appendix 1** for the complete Subject Instructions.

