6.3 Investigator Prescribed Rest Periods

Rest periods of several days may be prescribed by the investigator or designee to manage intense local skin reactions (LSRs). Treatment should resume as soon as possible after the skin reaction has subsided as determined by the investigator or designee. Neither 2-week treatment cycle should be extended beyond the 14 consecutive days due to rest periods or missed doses.

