17.3 Statistical Methods

All statistical processing will be performed using SAS® unless otherwise stated. The Safety population will include all randomized subjects who received the test article.

The Intent-to-Treat (ITT) population will include all randomized subjects who applied at least one dose of test article and returned for at least one post-baseline evaluation visit.

Subjects will be included in the PP efficacy analyses if they met all the inclusion/exclusion criteria, were compliant with the assigned test articles (applied at least 75% and no more than 125% of the test article applications and no other evidence of material dosing noncompliance), completed the evaluation at Week 14 within the designated visit window (± 4 days) with no protocol violations that would affect treatment evaluation. Subjects who are discontinued from the study due to lack of treatment effect or due to worsening condition that requires alternate or supplemental therapy for the treatment of AK should be included in the PP population as treatment failures (non-responders). Subjects discontinued prematurely for other reasons should be excluded from the PP population, but included in the ITT population using the Last Observation Carried Forward (LOCF) to impute missing values for efficacy variables.

Efficacy summaries and analyses will be carried out in the ITT and PP populations. All summaries of safety will be carried out in the safety population.

Demographic and baseline characteristics will be summarized by treatment group for the ITT and PP populations. The size of the treatment area (in centimeters) at baseline will be determined from an estimate of the % BSA treated. BSA will be determined from the subject's height and weight using the Mosteller formula. Frequency counts and percentages will be reported for categorical data. Sample size, mean, standard deviation, and minimum and maximum will be reported for the continuous variables.

Sponsor Name: Actavis, LLC Protocol: 094-3153-301, v1.0

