Temporary dosing interruptions (rest periods) may be instituted by the investigator as needed to manage LSRs or AEs. Treatment should be resumed upon adequate resolution as determined by the investigator. However, doses missed due to rest periods or for other reasons will not be made up and the duration of each dosing cycle must remain at 14 days. Dosing interruptions should be noted on the subject diary and documented in the subject's CRF (see **Section 6.3**).

A 2.7 Documentation of Test Article Application and Compliance

Subjects will be instructed to document the application of test article and any missed or held doses on the subject diary.

A 2.8 Return and Destruction of Test Article Supplies

At the completion or termination of the study, all unused and/or partially used test articles must be returned by a traceable method. All missing pumps must be explained on the completed Test Article Accountability Log. The investigator must keep the original Label pages and Test Article Accountability Log in the site study file. Photocopies of the original Test Article Accountability Log and Label pages will be kept with the study records at all shipment of returned test article must be labeled with the investigator's name, address, and the protocol number. Return all test article in the original containers by a traceable means (e.g., 2-day FedEx shipping) to:

Upon receipt of the test articles, a Sponsor representative will perform a final reconciliation. will be notified of any missing test article.

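### Does counting investigator-held doses against a fixed 28-dose denominator bias the per-protocol equivalence analysis?

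*SAP*

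**What the plan says.** **Rest periods.** Protocol 6.3 allows holds: "Rest periods of several days may be prescribed by the investigator or designee to manage intense local skin reactions (LSRs"). It gives no maximum number of days, but asks for treatment to resume as soon as the reaction has subsided and does not let a cycle run past 14 days. Section 6.2 says that once the 14 days have passed, "then no additional test article will be applied to make up for missed or held doses". Appendix 2 (A 2.6) repeats that "doses missed due to rest periods or for other reasons will not be made up".

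**Compliance and PP.** Under Protocol 17.3, PP subjects must have "applied at least 75% and no more than 125% of the test article applications", with no denominator named. The only visible denominator is in SAP 8.6.6: "The percent of expected doses will be calculated using 28 (once daily dosing for two 14 day treatment cycles"). One exception appears in Protocol 17.3: subjects discontinued for lack of effect, or for worsening that needs other AK therapy, "should be included in the PP population as treatment failures (non-responders").

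**What is analysed.** SAP section 7 states: "Efficacy summaries and analyses will be carried out in the ITT and PP populations". Under SAP 8.7.1, PP is primary and ITT supportive for equivalence. Applications, missed doses, held doses and percent of expected doses are summarised for both sets (8.6.6). PP and ITT membership is tabulated by arm (8.4), as are local skin reactions (8.8.2). Protocol deviations are listed (8.10), and under 8.1, "All data will be listed in subject data listings sorted by treatment group, site and subject number unless otherwise noted".

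**The concern.** A subject who stops for some days because the investigator said so is scored exactly like one who forgot. Two rest periods of four days, one in each cycle, reach 8 unapplied doses and remove the subject from the primary equivalence set. Holds are a response to skin reactions, and skin reactions are a response to the cream. If Test and Reference differ in irritation, the PP set could lose different kinds or numbers of subjects from the two arms. The comparison would then no longer be protected by randomisation.

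The supportive ITT analysis keeps such subjects, but it also restores every other PP exclusion and carries the last observation forward for missing values. If PP and ITT disagreed, ITT alone would not show whether the holds were the cause. No visible text plans a PP analysis that treats prescribed holds as compliant. At stake would be a false finding of equivalence, or a false failure.

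**Working it through.** **1. The cut-off.** Expected doses: 2 cycles × 14 days = 28, which reproduces the SAP figure. The lower limit is 0.75 × 28 = 21 applications.

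- 7 unapplied: 21/28 = 75.0%, in PP.
- 8 unapplied: 20/28 = 71.4%, out of PP.

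Held and missed doses count alike, so the first 7 prescribed holds cost nothing if no other dose is missed.

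**2. Possible size.** The documents give no frequency of holds, no clearance rates and no visible allocation ratio, so everything in this step is assumed. Let *a* be the true clearance rate in an arm (PP plus the hold-driven exclusions), *e* the share removed and *c* the clearance among those removed. The rate left in PP is

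p = (a − e·c)/(1 − e).

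Example: Test a = 0.10, e = 0.05, c = 0.60 gives p = 0.07/0.95 = 0.0737. Reference a = 0.30, e = 0.20, c = 0.60 gives p = 0.18/0.80 = 0.225. The true gap of 20.0 points appears as 15.1, so 4.9 points are hidden.

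The pass chance is the exact binomial probability that the 90% Wald interval with continuity correction 1/n lies within −0.20 to +0.20. Assumed n per active arm is 130 or 157: 435 split 1:1:1 (145) or 2:2:1 (174), less 10%. Holding n fixed isolates bias from loss of precision.

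| True Test / Reference | Removed Test / Reference | Clearance in those removed | PP difference | Pass chance, n = 130 / 157 |
|---|---|---|---|---|
| 50% / 30% | none | – | +20.0 points | 3.8% / 4.0% |
| 50% / 30% | 10% / 3% | 60% | +19.8 | 4.1% / 4.2% |
| 50% / 30% | 20% / 5% | 60% | +19.1 | 5.3% / 5.6% |
| 50% / 30% | 20% / 5% | 10% | +28.9 | below 0.1% |
| 50% / 30% | 5% / 20% | 10% | +17.1 | 9.2% / 10.8% |
| 10% / 30% | none | – | −20.0 | 3.7% / 3.9% |
| 10% / 30% | 3% / 10% | 60% | −18.2 | 8.1% / 9.0% |
| 10% / 30% | 5% / 20% | 60% | −15.1 | 24.9% / 29.2% |
| 10% / 30% | 5% / 20% | 40% | −19.1 | 5.6% / 6.1% |
| 30% / 30% | none | – | 0.0 | 91.8% / 96.5% |
| 30% / 30% | 10% / 3% | 60% | −2.4 | 90.6% / 95.4% |
| 30% / 30% | 20% / 5% | 60% | −5.9 | 79.6% / 86.5% |

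The largest false-pass figure needs a fourfold imbalance in exclusions (5% against 20%). It also needs 60% clearance among removed Test subjects when retained Test subjects clear at 7.4%, roughly an eightfold contrast within one arm. Lower that 60% to 40% and the figure falls to about 6%. With equal true clearance, the arms must differ in the share removed, or in clearance among those removed, before any bias arises.

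**3. Would the obvious remedy isolate the effect?** A natural sensitivity rule takes held doses out of the denominator: applications/(28 − held).

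- 1 held, 7 missed: 20/27 = 74.1%, still out and so labelled a missed-dose exclusion. Counting the hold as compliant gives 21/28 = 75.0%, so the hold alone caused the exclusion.
- 9 held, 5 missed: 14/19 = 73.7%, still out. Counting holds as compliant gives 23/28 = 82.1%.
- 22 held, 6 applied: 6/6 = 100%, admitted with 6/28 = 21.4% of scheduled doses.

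The rule misattributes some hold-driven exclusions and sets no exposure floor.

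**The case for a change.** The strongest case for acting is that the gap is real on the visible text and cheap to close. The rule penalises adherence to instructions, holds are tied to a treatment effect, held and missed doses are already recorded separately, and a definition fixed before unblinding is worth more than one reconstructed afterwards. The calculations also show that the decision can move in either direction when exclusions are very unequal.

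Most of this stands as description. The cut-off is read correctly, ITT cannot isolate the effect of holds, and a later breakdown from the listings would count as unplanned under SAP section 2.

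It does not show that the primary rule is wrong. A PP set is meant to hold subjects who received most of the scheduled exposure, and a subject with 20 of 28 doses did not, whatever the reason. Relaxing the rule has its own cost: subjects with little exposure may pull the two active arms together, so a favourable result in a widened set would reassure little. Nor can absence from the plan be established. The public SAP shows no PP definition in section 7 and no text under 8.5, the two places where a provision on holds would most naturally sit.

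**Conclusion.** No change to the plan is needed. Counting holds against 28 doses is a fair trade-off: it keeps the PP set tied to exposure, tolerates up to 7 unapplied doses for any reason, and applies identically to all arms. ITT subjects removed from PP by this rule remain in the planned ITT equivalence comparison, and those with an observed Visit 7 count need no carried-forward value there.

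The size is unknown, because the documents give no frequency of holds. Under the assumed rates and arm sizes, most scenarios move the chance of a false pass by a few points or lower it. Material distortion needs a large imbalance in exclusions combined with clearance among the excluded that differs sharply from the rest of their arm. Such an imbalance should be visible in outputs already planned: PP counts, held-dose summaries and skin-reaction tables by arm. An analyst who saw it could identify the subjects concerned from the listings, as those out of PP with (applied + held)/28 of at least 75%, and describe them in the study report. That is ordinary reporting practice and leaves the primary rule, the margin and the decision as they are. This conclusion rests on the visible text only.

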8.7 Efficacy Analyses

8.7.1 Primary Efficacy Analyses

The primary efficacy endpoint is the complete clearance rate (treatment success), defined as the proportion of subjects in the **PP** population at the EOS visit with 100% clearance of AK lesions in the Treatment Area. All AKs (baseline and new lesions) independent of size within the treatment area will be included in the efficacy lesion count for each visit.

The 90% Wald's confidence interval with Yate's continuity correction will be constructed on the difference (generic imiquimod minus Zyclara) in the proportions of subjects with complete lesion clearance to evaluate the therapeutic comparability of the two active treatments.

Two-sided, continuity-corrected Z-tests will be used to evaluate the superiority of each active treatment's complete clearance rate over that of the Vehicle treatment.

If the 90% confidence interval on the difference between the Test and Reference lesion complete clearance rates at EOS in the **PP** population is contained within the interval -0.20 to +0.20, and each of these proportions in the ITT population is greater than, and statistically different (p<0.05) from, the Vehicle proportion in the ITT population at EOS, then the Test and Reference products will be considered to be therapeutically equivalent.

The therapeutic comparability evaluations in the PP population will be considered primary while those in the ITT will be considered supportive. The superiority comparisons in the ITT population will be considered primary while those in the PP population will be considered supportive.

